#### 6.0 Statistical Analysis Methods

#### 6.1 General principles

The primary analyses will include adjustment for randomization strata (immunotherapy use and prednisone dose). Additional analyses that are unadjusted or are adjusted for potential confounders will also be performed as secondary analyses. Robust standard errors will be computed using statistical program-based approaches when available and a bootstrap with the individual as the sampling unit when a pre-programmed approach is not available. All statements of statistical significance and confidence intervals will be based upon a 2-tailed test with a 0.05 level of significance, unless stated otherwise. Key analyses will be duplicated by a second statistician. All analyses will be performed using SAS version 9 or higher, STATA or R.

Prior to formal testing, exploratory data analyses including graphical techniques (e.g. histograms, scatter-plots, boxplots, spaghetti and lasagna plots) and summary statistics (e.g. median, IQR, proportion) will be used to examine cross-sectional and longitudinal patterns in the data as well as identifying potential violations of the assumptions underpinning formal testing, which can help guide decisions to apply transformations or alternative methods. In some cases, transformations of raw data have already been identified (e.g. log-transformation for retinal thickness and IOP) and will be implemented. Summaries will be made overall and by treatment group. During model selection and formal testing, graphical (e.g. residual plots) and analytic (e.g. tests of normality, proportional hazards assumptions) methods will be used to detect violations of modeling assumptions.

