### 3.5 Eligibility criteria

#### Inclusion criteria

- 1. Age 13 years or older
- 2. Weight 30 kg (66 lbs) or greater
- 3. Active or recently active (≤ 60 days) non-infectious intermediate, posterior, or panuveitis
- 4. Prednisone indication meets one of the following:
  - a. Active uveitis requiring one of the following
    - i. Initiation of prednisone at dose greater than 7.5 mg/day
    - ii. Increasing prednisone dose to greater than 7.5 mg/day
    - iii. Currently receiving dose greater than 7.5 mg/day
  - b. Inactive uveitis on current dose greater 7.5 mg/day
- 5. Initiation or addition of an immunosuppressive drug (i.e., a conventional immunosuppressive drug or adalimumab) is indicated
- 6. If currently receiving a conventional immunosuppressive drug, the drug and dose have been stable for at least 30 days
- 7. Patient able and willing to self-administer subcutaneous injections or have a qualified person available to administer subcutaneous injections
- 8. If posterior segment disease is present, ability to assess activity in at least one eye with uveitis
- 9. Visual acuity of light perception or better in at least one eye with uveitis

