  - The initial dose of prednisone will be increased according to the current dose and the severity of the reactivation. For patients on more than half of the maximum allowed dose (i.e., maximum dose is 1 mg/kg/day up a maximum of 60 mg/day), the dose will be increased to the maximum allowed dose. For patients on less than half of the maximum allowed dose, the dose will be at least doubled but may be increased to any dose between double the current dose and the maximum allowed dose depending upon the severity of the disease. Should uveitis fail to be controlled after 2 weeks of this increased prednisone dose, then an additional 2 weeks of prednisone at the maximum dose, regardless of the initial dose, will be given. If the study ophthalmologist did not expect the uveitis to be controlled within 2 weeks, then the initial prednisone period may be 4 weeks. To avoid complications of systemic corticosteroid therapy, prednisone tapering will be initiated at week 4 per section 4.2.2. At V02 if the uveitis is neither controlled nor substantially improved such that it is expected to be inactive at the next visit (V03 in 4 weeks), then, immunosuppression will be advanced per section 4.4. Additional advancement of the immunosuppressive treatment will be implemented according to the guidelines in section 4.4. until inflammation is controlled or else the best medical judgment point on the immunosuppression guidelines is reached.

• Patients with recently active but inactive uveitis by enrollment on prednisone >7.5 mg/day:

The dose will be held at that level (i.e., the >7.5 mg/day dose patient was on at enrollment) for 4 weeks after initiating the new immunosuppressive agent to enable that agent to have an effect. Prednisone tapering will be initiated at week 4. Should the patient's uveitis become active within those four weeks, they will be managed as described in the preceding bullet.

Table 4. Initial prednisone dosing summary							
Status at enrollment	Initial dose (Week 0)	First opportunity to taper *† (Week 2)	Second opportunity to taper (Week 4)				

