#### 6.3 Primary outcome analysis

The primary goal of the trial is to establish whether adalimumab is superior to conventional immunosuppression for corticosteroid-sparing in the treatment of individuals with intermediate, posterior, or pannuveitis. The analysis will focus on the cumulative proportion with a success. Once a success has been achieved, then it will remain fixed for that individual thereafter. A more standard time to event analysis, which allows for censoring due to loss to follow-up, was considered. However, because the time required to taper prednisone to  $\leq 7.5$  mg/day depends substantially on the initial prednisone dose, small imbalances at baseline could influence greatly such analyses despite stratification. Therefore, time to event analyses will be used as sensitivity analyses. The 6-month time frame was chosen to allow sufficient time to observe the primary outcome regardless of the participant's prednisone dose at randomization and is likely to be more robust to imbalances. Multiple imputation will be used to address missing data due to missed interim visits and loss to follow-up.

Since a minimum of two follow-up visits must occur prior to achieving a corticosteroid success and prednisone must be tapered, the first outcome evaluation will occur at 2 months (V03) and will continue for every visit thereafter. Modeling will focus upon the period between 6 months and 1 year due to the potential for imbalances in the tapering patterns described above. Generalized estimating equations (GEE) will be used to fit logistic regression models comparing the two treatment groups over time while accounting for the correlation between replicate measurements. A saturated mean structure including visits starting at 6 months (V07-V10), treatment, and visit by treatment interaction terms plus the two stratification variables (baseline immunotherapy and initial prednisone dose) will be used. The mean model structure is:

$$logit(Y) = \beta_0 + \beta_1 A + \beta_2 P + \beta_3 S + \beta_4 V_7 + \beta_5 V_8 + \beta_6 V_9 + \beta_7 V_{10} + \beta_8 I_7 + \beta_9 I_8 + \beta_{10} I_9 + \beta_{11} I_{10}$$

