where Y indicates the outcome (0: no corticosteroid sparing success, 1: corticosteroid sparing success), A indicates treatment (0: conventional immunosuppression, 1: adalimumab), P is an indicator of prednisone dose stratum (0: < 30mg/day, 1:  $\geq$  30 mg/day), S is an indicator of baseline immunotherapy stratum (0: none; 1: one),  $V_j$  is an indicator for visit j ( $j \in 7, ...10$ ), and  $I_j$  is an indicator for the visit by treatment interaction term for the  $j^{th}$  visit. An unstructured correlation matrix will be used to model the within-individual repeated measurements. Alternate correlation structures (e.g. exchangeable) will be explored if the unstructured covariance matrix is unstable. This model estimates the relative odds of corticosteroid-sparing for adalimumab vs conventional immunosuppression. The primary outcome will be represented by  $exp(\beta_1A + \beta_8I_7)$ , i.e. the odds ratio of the cumulative proportion for adalimumab vs conventional immunosuppression at six months (i.e. V07).

A standardized estimator, which allows for covariate adjustment, will be used to compare the absolute (as opposed to relative) difference in proportions at each time-point based upon the logistic model described above. This estimator has the advantage of providing a consistent estimate even if the means model is misspecified. For each participant, the probability of a corticosteroid-sparing success at each time point is computed under two scenarios to create the counter-factual probabilities: (a) as if the participant had been assigned to adalimumab and (b) as if the participant had been assigned to conventional immunosuppression. Next, the average probabilities are computed for each group and the absolute treatment effect is calculated by taking the difference. The bootstrap will be used to calculate 95% confidence intervals and p-values. The equivalence margin is defined to be 5%.

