## 6.4 Analysis of additional outcomes

The analyses of prednisone sparing success, an important secondary outcome, will be analyzed using the methods described for the primary outcome in Section 6.3 with the focus on the cumulative proportion at 1 year. Most of the remaining outcomes will be analyzed using longitudinal analysis techniques or event analysis techniques. Table 2 summarizes the outcome type and corresponding analysis technique for these outcomes with safety outcomes highlighted in italics. Additional details of safety monitoring are provided in Section 7.2.

Table 2. Summary of the type, modeling and frequency of secondary and safety outcomes for the ADVISE trial.							
Outcome Type	Modeling Techniques	Visit Intervals	ADVISE Outcomes				
Continuous							
Person-level	GEE with a linear link Linear mixed effects models	V01-V10 V01, V04, V07, V12	Prednisone dose QoL outcomes (EQ-5D, SF-36, NEI-VFQ)				
Eye-level	GEE with a linear link and bootstrap CIs Linear mixed effects models with a person-specific random intercept	V01-V10 V01, V04, V07, V12	Visual acuity Retinal thickness (log-scale)				
Binary							
Person-level	GEE with a logistic link	V01-V10 V02-V10	Individual level activity (no activity in either eye) Prednisone dose ≤ 7.5 mg				
Eye-level	GEE with a logistic link and bootstrap CIs	V01-V10 V01, V04, V07, V12 V02-V10 V04, V07, V12	Prednisone haltedVA 20/40 or betterVA worse than 20/200Uveitis activityMacular edema (≥ 260µm)Improvement in macular edemaResolution of macular edemaWorsening of macular edema				
Event rates							
Person-level	Negative binomial regression	Real time post randomization	Hospitalization Infections requiring antimicrobial therapy Type-specific infections SAEs				
Time to first event							
Person-level	Kaplan-Meier estimates Cox proportional hazards models	Real time post randomization	Death Hospitalization Infections requiring antimicrobial therapy Type-specific infections SAEs Other Systemia Events				
Eye-level	Frailty models	V02-V10 V02-V10 V04, V07, V12	Decline in VA $\geq$ 6 lines or to NLP or LP New onset macular edema				

Evaluations of repeated binary outcomes (e.g activity, macular edema) and continuous outcomes (e.g. visual acuity) over time will be analyzed using generalized estimating equations (GEE) with Gaussian or logit links

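### The primary model omits baseline uveitis activity, which is already recorded and is part of the outcome: a cheap improvement, not an error

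*SAP*

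**What the plan says.** SAP 6.1 sets the rule for primary analyses: "The primary analyses will include adjustment for randomization strata (immunotherapy use and prednisone dose". SAP 6.3 applies it. The logistic GEE for V07-V10 contains treatment, visit and their interaction, "plus the two stratification variables (baseline immunotherapy and initial prednisone dose) will be used". The primary effect is read off at V07, "i.e. the odds ratio of the cumulative proportion for adalimumab vs conventional immunosuppression at six months".

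The absolute effect comes from the same model: "A standardized estimator, which allows for covariate adjustment" is used to compare proportions at each time point, so its covariates are also the two strata. For the repeated measures, "An unstructured correlation matrix will be used to model the within-individual repeated measurements".

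Other covariates enter only secondary analyses. Protocol 8.3 names age, gender, race and uveitis class in an open list. Baseline activity is not named there, is not a stratification factor, and is not among the planned subgroups in SAP 6.5.

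Activity nevertheless varies at entry and is available. Protocol 3.5 admits patients with active disease and also those with "Inactive uveitis on current dose greater 7.5 mg/day". SAP 6.4, Table 2, lists "Individual level activity (no activity in either eye" as a person-level outcome from V01. SAP 4.1 makes inactive uveitis one of the two components of success.

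**The concern.** A baseline version of an outcome component is a natural covariate to pre-specify. If it predicts success, leaving it out of the standardized estimator gives up precision that costs no new data.

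The prednisone stratum carries part of this information, but not all of it (Protocol 4.2.1):

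- Active patients not on prednisone start at the maximum allowed dose. With the 30 kg weight minimum, that puts them in the stratum at or above 30 mg/day.
- Reactivated patients can land in either stratum: "For patients on less than half of the maximum allowed dose, the dose will be at least doubled", with the final dose depending on severity.
- Inactive patients hold whatever dose above 7.5 mg/day they were on at enrollment.

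Both dose strata can therefore mix active and inactive patients. At stake is some variance of the risk difference and a little power, not validity.

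**Working it through.** **1. The plan's own figure.** SAP 6.2 gives 46.1% vs 67.5%, 111 per arm, two-sided 0.05.

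- Sum of variances: 0.461×0.539 + 0.675×0.325 = 0.248479 + 0.219375 = 0.467854. SE = √(0.467854/111) = 0.06492.
- Pooled: mean rate 0.568, null SE = √(2×0.568×0.432/111) = 0.06649. z = (0.214 − 1.96×0.06649)/0.06492 = 1.289, power 90.1%.
- Unpooled: z = 0.214/0.06492 − 1.96 = 1.336, power 90.9%.

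The stated 90% reproduces.

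**2. Assumed inputs.** The documents give none of these: share inactive q = 15-50%; success gap d = 5-30 points, equal in both arms; partial dose proxy, with 70% of inactive and 30% of active patients starting below 30 mg/day. The immunosuppression stratum is left out of this step.

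**3. Formula.** Adjustment removes the between-group variance B from each arm: variance = (0.467854 − 2B)/111.

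- Adjusting for activity: B = q(1−q)d².
- Adjusting for dose stratum only: B = s(1−s)(dΔ)², where s is the share below 30 mg/day and Δ is the difference between the dose strata in the share inactive.

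**4. Central case (q = 0.40, d = 0.20).**

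- s = 0.4×0.7 + 0.6×0.3 = 0.46. Δ = 0.28/0.46 − 0.12/0.54 = 0.3865.
- Dose only: B = 0.46×0.54×(0.0773)² = 0.001484. Variance sum 0.464886, SE 0.06472, z = 3.307 − 1.96 = 1.347, power 91.1%.
- Activity: B = 0.24×0.04 = 0.0096. Variance sum 0.448654, SE 0.06358, z = 3.366 − 1.96 = 1.406, power 92.0%.
- Fall: 1 − 0.448654/0.464886 = 3.5%, or about 8 of 222 patients. Assuming a constant odds ratio instead of an equal gap gives 3.0%.

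**5. Range, same formula.**

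| Inactive | Gap | s, Δ | Variance sum, dose only | Variance sum, activity | Fall |
|---|---|---|---|---|---|
| 15% | 5 | 0.36, 0.221 | 0.46780 | 0.46722 | 0.1% |
| 50% | 10 | 0.50, 0.40 | 0.46705 | 0.46285 | 0.9% |
| 40% | 20 | 0.46, 0.386 | 0.46489 | 0.44865 | 3.5% |
| 50% | 30 | 0.50, 0.40 | 0.46065 | 0.42285 | 8.2% |

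A stronger proxy (85% vs 20% below 30 mg/day) caps the fall at 5.8%. No proxy, the least plausible case, caps it at 9.6%. A separate calculation that included the immunosuppression stratum, on a somewhat different grid of assumptions, gave 0.06-9.7%.

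**6. Odds-ratio scale.** In the central case with a constant odds ratio, the log-odds-ratio SE rises from 0.279 to 0.284 and the conditional odds ratio moves from 2.44 to 2.51. Power goes from 89.2% (ln 2.44/0.279 − 1.96 = 1.24) to 90.0% (ln 2.51/0.284 − 1.96 = 1.28). Over the partial-proxy grid the SE rises 0.1-4.7% and power gains 0-2.1 points.

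**7. Simulation of the planned GEE** (unstructured correlation, constant activity coefficient, 6,000 trials per setting, 30-50% inactive, gaps 10-30). Variance at V07 fell 0.5-7.8%, and power rose 0.3-1.9 points over the two scales. At 50% inactive and gap 30, the standardized risk difference drifted from 0.2117 to 0.2086 (true value 0.2138), because the simulated activity effect fades after V07. With visit-specific coefficients it went from 0.2124 to 0.2127.

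**8. Closer to the recommended model.**

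- Visit-specific GEE, 2,200 trials: the variance fall was 6.5% at 50/30 (percent inactive/gap in points) and 0.5% at 40/20.
- V07 only: falls of about 0%, 3% and 6-7% at 30/10, 40/20 and 50/30, with null rejection 4.7-5.7%.

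**9. Multiple imputation** (10% lost, 51% vs 75%, 1,000 trials). Empirical variance fell 0.0% at 40/10, 1.1% at 40/20, −0.3% at 40/20 with loss depending on activity, and 7.8% at 50/30. Only the last is distinguishable from zero. Power started at 94.6-94.9% and rose 0.1-0.2 points, or 0.8 at 50/30. Bootstrap intervals and outcome-dependent loss were not modelled.

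**The case against.** The strongest reply is that nothing here is broken. Adjusting for the randomization strata is a legitimate pre-specified choice, and the plan could equally have picked visual acuity, macular edema or uveitis class. The first half stands. On the second, activity has the better claim, because it is a component of the endpoint and drives the initial prednisone rule.

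Next, every size above rests on assumed inputs, and the design points toward weak prognosis. Inactive entrants must have been active within 60 days and still be above 7.5 mg/day. Protocol 4.2.2 expects a 60 mg/day starter to reach the outcome by 15 weeks. The 6-month window was chosen to suit any starting dose. This stands, and it is why the lower part of the range should be taken seriously.

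Third, the visit-specific run at 40/20 showed a variance fall of only 0.5% while its power moved from 90.4% to 91.7%. A 0.5% fall would explain only about 0.1 point of that, so the run is noisy. The V07-only result of about 3% agrees with the formula, but imputation shrinks the gain in most settings.

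Fourth, secondary adjusted analyses with an open covariate list could already include activity. True, but an unnamed secondary analysis neither improves the primary one nor guards against choosing covariates after the fact.

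A reader might infer from the omission that the primary result will be biased or the trial underpowered. The documents do not support that: randomization protects the comparison, and the stated power reproduces without this covariate. Nor should a reader infer that the odds ratio becomes more precise. Its SE rises, and only power improves, slightly.

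**Conclusion.** The omission is real and worth correcting while that can be done cleanly, but it is a cheap improvement of low severity. The planned analysis is valid. With 15-50% inactive, a 5-30 point gap and a partial dose proxy, the risk-difference variance falls by about 1% or less for gaps up to 10 points and by about 3% at 40% inactive with a 20-point gap. It approaches 8% only with a gap near 30 points and an even split. Reading 8% as the expected gain would be unsupported, since the documents give neither the inactive share nor its prognostic strength. Power gains are about 0-2.5 points on either scale and about 0.1-0.8 under the planned imputation.

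**What to change.** By a dated amendment made without reference to by-arm outcomes:

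- Add one covariate, baseline activity (active in either eye vs inactive), with visit-specific coefficients, to the SAP 6.3 model and its standardized estimator.
- Add it to the primary-outcome imputation model in SAP 6.7.
- Align SAP 6.1 and Protocol 8.3.
- Report the standardized risk difference alongside the odds ratio.

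Timing matters because treatment is unmasked and, under SAP 7.0 and 7.3, the Coordinating Center prepares efficacy and safety reports for the monitoring committee. If those deciding have already seen by-arm outcomes, name this as a pre-specified sensitivity analysis instead; the existing text allows it.

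The cost is an amendment to two documents, up to four extra parameters, a slightly larger log-odds-ratio SE, and a small shift of the conditional odds ratio away from 1 (from about 2.43 to 2.44-2.64 for gaps of 10-30 points). No new data are needed. The simulations showed no clear type I error inflation: with a constant coefficient, final-test rejection went from 5.0% to 4.8% at 40/20 and from 5.1% to 5.5% at 50/30 (Monte Carlo SE 0.3 points).

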#### 6.3 Primary outcome analysis

The primary goal of the trial is to establish whether adalimumab is superior to conventional immunosuppression for corticosteroid-sparing in the treatment of individuals with intermediate, posterior, or pannuveitis. The analysis will focus on the cumulative proportion with a success. Once a success has been achieved, then it will remain fixed for that individual thereafter. A more standard time to event analysis, which allows for censoring due to loss to follow-up, was considered. However, because the time required to taper prednisone to  $\leq 7.5$  mg/day depends substantially on the initial prednisone dose, small imbalances at baseline could influence greatly such analyses despite stratification. Therefore, time to event analyses will be used as sensitivity analyses. The 6-month time frame was chosen to allow sufficient time to observe the primary outcome regardless of the participant's prednisone dose at randomization and is likely to be more robust to imbalances. Multiple imputation will be used to address missing data due to missed interim visits and loss to follow-up.

Since a minimum of two follow-up visits must occur prior to achieving a corticosteroid success and prednisone must be tapered, the first outcome evaluation will occur at 2 months (V03) and will continue for every visit thereafter. Modeling will focus upon the period between 6 months and 1 year due to the potential for imbalances in the tapering patterns described above. Generalized estimating equations (GEE) will be used to fit logistic regression models comparing the two treatment groups over time while accounting for the correlation between replicate measurements. A saturated mean structure including visits starting at 6 months (V07-V10), treatment, and visit by treatment interaction terms plus the two stratification variables (baseline immunotherapy and initial prednisone dose) will be used. The mean model structure is:

$$logit(Y) = \beta_0 + \beta_1 A + \beta_2 P + \beta_3 S + \beta_4 V_7 + \beta_5 V_8 + \beta_6 V_9 + \beta_7 V_{10} + \beta_8 I_7 + \beta_9 I_8 + \beta_{10} I_9 + \beta_{11} I_{10}$$

where Y indicates the outcome (0: no corticosteroid sparing success, 1: corticosteroid sparing success), A indicates treatment (0: conventional immunosuppression, 1: adalimumab), P is an indicator of prednisone dose stratum (0: < 30mg/day, 1:  $\geq$  30 mg/day), S is an indicator of baseline immunotherapy stratum (0: none; 1: one),  $V_j$  is an indicator for visit j ( $j \in 7, ...10$ ), and  $I_j$  is an indicator for the visit by treatment interaction term for the  $j^{th}$  visit. An unstructured correlation matrix will be used to model the within-individual repeated measurements. Alternate correlation structures (e.g. exchangeable) will be explored if the unstructured covariance matrix is unstable. This model estimates the relative odds of corticosteroid-sparing for adalimumab vs conventional immunosuppression. The primary outcome will be represented by  $exp(\beta_1A + \beta_8I_7)$ , i.e. the odds ratio of the cumulative proportion for adalimumab vs conventional immunosuppression at six months (i.e. V07).

A standardized estimator, which allows for covariate adjustment, will be used to compare the absolute (as opposed to relative) difference in proportions at each time-point based upon the logistic model described above. This estimator has the advantage of providing a consistent estimate even if the means model is misspecified. For each participant, the probability of a corticosteroid-sparing success at each time point is computed under two scenarios to create the counter-factual probabilities: (a) as if the participant had been assigned to adalimumab and (b) as if the participant had been assigned to conventional immunosuppression. Next, the average probabilities are computed for each group and the absolute treatment effect is calculated by taking the difference. The bootstrap will be used to calculate 95% confidence intervals and p-values. The equivalence margin is defined to be 5%.

Sensitivity analyses will be used to explore the alternate quantifications and robustness of the comparisons between the two groups. Longitudinal assessments of the components of corticosteroid sparing (activity and prednisone dose  $\leq$  7.5 mg/day) will be performed. In addition, time to event analyses will be used to assess the duration of success. Details of these modeling techniques are described in section 6.4. In addition, a variety of missing data techniques (Section 6.7) will be used to assess the potential impact of both interim missed visits and loss to follow-up.

